6.2. Exclusion Criteria

Patients will be excluded from study enrollment if they meet any of the following criteria at Visit 1, unless stated otherwise in respective criterion:

19. Are currently enrolled in any other clinical study involving an investigational product or any other type of medical research judged not to be scientifically or medically compatible with this study.
20. Have participated, within the last 30 days or 5-half-lives (whichever is longer), in a clinical study involving any investigational product. If the half-life of the investigational product is unknown, 6 months should have passed prior to Visit 1.
21. Have previously completed or withdrawn from this study or any other study investigating LY3451838.
22. Known hypersensitivity or intolerance to monoclonal antibodies or other therapeutic proteins, or to common antihistamines, epinephrine, methylprednisolone or other systemic corticosteroids.
23. Are currently receiving medication or other treatment for prevention of migraine headaches. Patients must have discontinued such medications or treatments at least 2 weeks prior to Visit 2. Botulinum toxin A and B that has been administered in the head or neck area use must be discontinued at least 3 months prior to Visit 2. Nerve blocks or device use (such as transcranial magnetic stimulation or electrical nerve stimulation) in the head or neck area for migraine treatment must be discontinued at least 30 days prior to Visit 2. Anti-CGRP antibodies (to either ligand or receptor) must be discontinued at least 5 half-lives prior to Visit 2.
24. Have previously failed more than 4 migraine preventive medication categories in the past 10 years from the medication list in Inclusion Criterion # 6 due to inadequate efficacy (that is, maximum tolerated dose for at least 2 months) and/or safety/tolerability reasons. Previous failures to medications not on the above list will not be considered toward this exclusion.

25. History of cluster headache or migraine subtypes including hemiplegic (sporadic or familial) migraine, ophthalmoplegic migraine, retinal migraine, typical aura without headache, complications of migraine and migraine with brainstem aura (basilar-type migraine) defined by IHS ICHD-3.

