## 5.3. Handling of Dropouts or Missing Data

Missing data imputation for adverse event medical history, and concomitant medication dates will be performed as follows. Imputed dates will be used to determine treatment-emergent or concomitant status, but imputed portions of dates (or times) will not be displayed in listings.

Start dates/Dates of onset:

- Completely missing: impute as patient's treatment date
- Year present, month and day missing:
  - o If year is the same as year of treatment date, impute as treatment date
  - o Otherwise, impute as December 31st
- Month and year present, day missing:
  - o If month and year are the same as treatment date, impute as treatment date
  - o Otherwise, impute as last day of the month
- Time missing:
  - o If same date as treatment date, impute as start time of treatment
  - o Otherwise impute as 23:59

End dates / resolution dates:

- Completely missing: impute as date of study completion or withdrawal from study
- Year present, month and day missing: Impute as December 31st
- Month and year present, day missing: Impute as the last day of the month
- Time missing: Impute as 23:59

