## **5.7. Demographics and Baseline Characteristics**

The following will be summarized by treatment group using the FAS.

- Demographics (age, sex, ethnic origin, race)
- Baseline characteristics (height, weight, body mass index)
- Migraine and/or headache-related measures from the ePRO diary per 1-month baseline period
  - Number of monthly migraine headache days
- Number of prior migraine preventive treatment failures from the list in protocol Section 6.1 (Inclusion Criterion #6):
- Medical history and pre-existing conditions

Medical history and preexisting conditions will be summarized by descending frequency of preferred term (PT) within system organ class (SOC). Medical history is defined as illness(es) that ended prior to the signing of informed consent. Preexisting conditions are defined as either ongoing (concomitant) or has ended (prior) on or after the date of informed consent.

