## 5.10. Concomitant Therapy

[figure not shown]
The proportion of patients who received concomitant medication and acute medications will be summarized and listed using the FAS. Concomitant medication refers to medication used to prevent migraines. The list of concomitant medication is found in section 7.8 of the protocol table 7.1.

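### SAP 5.3 has no end-date rule for items already over at entry: a wholly missing stop date, or a year-only one in the dosing or consent year, makes them look current in descriptive tables

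*SAP*

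**What the plan says.** The scope sentence of SAP 5.3 reads "Missing data imputation for adverse event medical history, and concomitant medication dates will be performed as follows". These dates are not only for display: "Imputed dates will be used to determine treatment-emergent or concomitant status". The end-date rules are:

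- Wholly missing: "Completely missing: impute as date of study completion or withdrawal from study".
- Year only: "Year present, month and day missing: Impute as December 31".
- Month and year only: "Month and year present, day missing: Impute as the last day of the month".

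The section has no branch for an item recorded as already stopped, no distinction between ongoing and ended on an unknown date, and no cap on the two partial-date rules.

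Two other SAP sections matter. SAP 5.7 files illnesses by end date: "Medical history is defined as illness(es) that ended prior to the signing of informed consent". An illness that is ongoing, or that ended on or after the consent date, is a preexisting condition instead. SAP 5.10 summarizes concomitant therapy and says "Concomitant medication refers to medication used to prevent migraines", pointing to protocol Table 7.1; the text available to us gives no date cut-off.

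On the protocol side, Inclusion Criterion 6 requires failure of 2 to 4 preventive categories in the past 10 years, and a physician's confirmation is enough documentation. Exclusion Criterion 23 says "Patients must have discontinued such medications or treatments at least 2 weeks prior to Visit 2". Section 7.8 bars preventives throughout treatment and follow-up.

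**The concern.** Late imputation of an end date is sensible for adverse events and for items that may be continuing. It is not sensible for a drug or illness that the record itself shows had ended before the patient entered.

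Every patient here has a history of stopped preventives reaching back up to 10 years, so some stop dates may well be vague. Because SAP 5.10 counts preventives, and preventives are forbidden after entry, the true figure in that table should be near zero. A stopped drug carried forward by the rule would read as a breach of the concomitant-therapy restrictions. In the same way, a resolved illness would move from the medical history table to the preexisting condition table.

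**Working it through.** No figure in the plan addresses this point, so there is none to reproduce. The check applies the three rules to items that truly ended before entry.

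**Inputs from the documents.** Consent is at Visit 1 (SAP Table 5.1). Visit 2 follows by 3 to 90 days, and dosing at Visit 3 comes at least 30 days after Visit 2 (protocol Schedule of Activities). Follow-up runs to 140 days after dosing (protocol 5.1). The look-back is 10 years (Criterion 6).

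**Wholly missing.** The imputed end is completion or withdrawal. For a dosed patient this is on or after dosing, so 100% of such items are derived as present after consent and after dosing.

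**Year only.** The imputed end is 31 December of the stop year, which cannot precede any date in that year. Status is therefore wrong against dosing exactly when the stop year is the dosing year, and wrong against consent exactly when it is the consent year. For all earlier years it is right.

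**Month and year.** The shift is at most 30 days (day 1 to day 31).

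- An illness that ended before consent ended more than 3 + 30 = 33 days before dosing, so it cannot cross dosing.
- A preventive stopped 14 days before Visit 2 has a gap of at least 14 + 30 = 44 days. Protocol 7.8 gives 5 days rather than 2 weeks; these passages need reconciling, but 5 + 30 = 35 days also exceeds 30.
- Against consent, an error is possible only when the stop month is the consent month.

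**Example.** Take consent on 15 June 2021 and dosing 65 days later (assumed), on 19 August 2021. Completion 140 days after dosing is 6 January 2022.

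| Recorded stop | Imputed end | After consent? | After dosing? |
|---|---|---|---|
| none | 6 Jan 2022 | yes (wrong) | yes (wrong) |
| 2019 | 31 Dec 2019 | no | no |
| 2020 | 31 Dec 2020 | no | no |
| 2021 | 31 Dec 2021 | yes (wrong) | yes (wrong) |
| May 2021 | 31 May 2021 | no | no |
| June 2021 | 30 June 2021 | yes (wrong) | no |

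**Share of partial dates that go wrong.** Assumptions, not in the documents: consent dates spread over one calendar year (taken weekly), dosing 65 days after consent, true stops spread evenly over the window before consent.

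| Window | Year only, vs consent | Year only, vs dosing | Month-year, vs consent | Month-year, vs dosing |
|---|---|---|---|---|
| 1 year | 49.9% | 32.7% | 4.0% | 0% |
| 2 years | 24.9% | 16.3% | 2.0% | 0% |
| 10 years | 5.0% | 3.3% | 0.4% | 0% |

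The consent column can be checked by hand. On average half of the consent year has passed, so the share is 0.5/1, 0.5/2 and 0.5/10, or 50%, 25% and 5%. For the 10-year window it runs from 0.4% with consent in mid-January to 9.5% in mid-December.

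**No cap.** With dosing on 15 March 2021, completion is 140 days later, on 2 August 2021. A year-only stop of 2021 is imputed to 31 December, 151 days after the patient left the study. A record with no date at all would get an earlier end than this one with a known year.

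**The case against.** The strongest reply is that this is conservative date programming for descriptive tables. Much of that stands. The migraine-day endpoint comes from the ePRO diary. The affected records predate randomization, so no difference between arms is expected. SAP 5.3 keeps imputed portions out of listings, so a listing would show the blank stop date and a reader could spot the artefact. Important deviations are reviewed before unblinding under criteria held in another document (SAP 5.6), and nothing says imputed dates feed that review.

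It is also fair that SAP 5.10 defines concomitant medication by use, that a figure in that section is not visible to us, and that prior failures are summarized separately as a baseline characteristic. They may never enter the medication derivation. But SAP 5.3 says imputed dates determine concomitant status, so some date cut-off is implied, and its absence is itself worth repairing. Conservatism does not justify overriding a recorded stop.

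A reader might infer three stronger things that the documents do not support:

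- **That every missing or partial stop date is misclassified.** Only wholly missing dates go to study completion, and the partial rules fail only in the cases set out above.
- **A patient count.** If 2%, 5% or 10% of prior-preventive records lacked a stop date, with 3 per patient, 1 − (1 − p)³ gives 5.9%, 14.3% or 27.1% of patients. Neither that rate nor the recording of prior failures as dated medications is documented. Multiplying by the planned 60 is not safe either, because SAP 5.11.4 reports insufficient enrollment.
- **That a recurrence after infusion is hidden as non-treatment-emergent.** SAP 5.12.1 compares severity with baseline per Lowest Level Term, but does not say that resolved history supplies that baseline or that severity is collected for it.

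**Conclusion.** The point holds in a limited form. Read literally, SAP 5.3 always gives the wrong status against dosing to an item that ended before entry with a wholly missing stop date, and to one with a year-only stop in the dosing year. It gives the wrong status against consent when the year-only stop is in the consent year. Other year-only stops are right, and month-year stops are right against dosing.

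The reach is the SAP 5.7 history and preexisting condition tables and, to the extent that stopped preventives are recorded with medication dates, the SAP 5.10 table. The 3% and 5% figures depend on evenly spread stops over 10 years and apply only to year-only records. The number of affected records is unknown. No effect on the primary endpoint or on treatment-emergent events is shown. It is worth correcting because the repair is cheap and a false count of prohibited preventives would be hard to explain.

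**What to change.** Amend SAP 5.3 so that recorded status limits the imputed end date:

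- Impute to study completion or withdrawal only if the record is marked ongoing or its status is unknown. This keeps real breaches visible.
- If the record shows the item ended before informed consent, use the earlier of the current rule and the day before consent. A limit at Visit 1 would not do: Visit 1 is the consent date, and SAP 5.7 treats an illness ending on that date as preexisting.
- If the record shows a preventive was stopped during screening, set the imputed end no later than the day before Visit 2. Protocol 5.1 foresees this route, since consent must precede stopping excluded medications.
- Cap every imputed end date at study completion or withdrawal.
- Do not let an imputed start date fall after the end date. Otherwise a wholly missing start, which SAP 5.3 sets to the treatment date, would follow an end date limited as above.

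In SAP 5.10, state the date cut-off that makes a medication concomitant, for example taken on or after the dosing date.

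The cost is a few lines of SAP text and a small change to the date-derivation program. The downside is reliance on the recorded ongoing or stopped status. SAP 5.11.2 already reports observed diary compliance, so the sponsor may be able to count the affected records now and state how many change.

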## **5.4. Multiple Comparisons/Multiplicity for Endpoints**

No adjustment for multiplicity is planned for this study.

## **5.5. Patient Disposition**

A summary and listing of patient disposition using the FAS will be provided at the end of the study. All patients who discontinue from the study will be identified in the listing. If known, a reason for their discontinuation will be given in the listing.

## **5.6. Protocol Deviation**

Important protocol deviations are defined as deviations from the protocol that potentially could have a meaningful impact on study conduct or on the primary efficacy, safety, or pharmacokinetics (PK) outcomes for an individual participant. The criteria for identifying study important protocol deviations will be defined within the appropriate protocol-specific document and will be reviewed as part of the ongoing data cleaning process and data evaluation.

All important protocol deviations will be identified and documented prior to unblinding to confirm exclusion from the PPS. A summary and a listing of all important protocol deviation will be produced using the FAS.

## **5.7. Demographics and Baseline Characteristics**

The following will be summarized by treatment group using the FAS.

- Demographics (age, sex, ethnic origin, race)
- Baseline characteristics (height, weight, body mass index)
- Migraine and/or headache-related measures from the ePRO diary per 1-month baseline period
  - Number of monthly migraine headache days
- Number of prior migraine preventive treatment failures from the list in protocol Section 6.1 (Inclusion Criterion #6):
- Medical history and pre-existing conditions

Medical history and preexisting conditions will be summarized by descending frequency of preferred term (PT) within system organ class (SOC). Medical history is defined as illness(es) that ended prior to the signing of informed consent. Preexisting conditions are defined as either ongoing (concomitant) or has ended (prior) on or after the date of informed consent.

## 5.8. Treatment Compliance

The study drug will be administered at the site during Visit 3. Drug administration information will be listed. All patients will receive CCI of either the treatment or placebo. Patients will be classified as receiving the complete drug administration if they receive all CCI

## 5.9. Electronic Patient Reported Outcomes Diary Compliance

Electronic patient reported outcomes diary compliance at each 1-month period (including baseline and 1-month treatment phase) will be calculated. Diary compliance at each period is calculated as:

Actual number of diary days in the period / Expected number of diary days in the period \* 100

Diary compliance is defined using an 80% threshold.

A summary of diary compliance will be produced by treatment arm using the FAS.

## 5.10. Concomitant Therapy

[figure not shown]
The proportion of patients who received concomitant medication and acute medications will be summarized and listed using the FAS. Concomitant medication refers to medication used to prevent migraines. The list of concomitant medication is found in section 7.8 of the protocol table 7.1.

## 5.11. Efficacy Analyses

### 5.11.1. Primary Endpoint and Primary Methodology

The primary analysis will be performed using a linear model for the change from baseline in the monthly number of migraine headache days within the Bayesian framework. The model will include randomized treatment and type of migraine as fixed effects and the baseline number of monthly migraine headache days as a covariate. The analysis will use a non-informative prior for the treatment effect. CCI

The logo consists of the letters 'CCI' in a large, bold, red sans-serif font. The letters are slightly overlapping, with 'C' on the left, 'C' in the middle, and 'I' on the right. The background is a solid black rectangle.

Additionally, if the compliance rate for a monthly interval is  $\leq 50\%$ , then the number of migraine headache days derived from the ePRO diary data for that 1-month period will be considered missing.

### **5.11.2. Sensitivity Analyses for Primary Endpoint**

All patients have over 50% diary entry compliance in the 1-month treatment phase and no subject has monthly migraine headache days set to missing. Therefore, the sensitivity analysis will not be performed.

### **5.11.3. Supplemental Analysis on the Primary Endpoint**

A second supplemental analysis for the primary endpoint will include a change in baseline for monthly migraine headache day using post-baseline data to month 3. The 3-month migraine headache days will be normalized to 30 days as done with the 1-month treatment phase data.

#### **5.11.4. Secondary and Exploratory Efficacy Endpoints**

Due to insufficient enrollment only the primary endpoint is to be evaluated. The data for all secondary and exploratory endpoints is available in the SDTMs for any analyses to be performed if needed.

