9.1.2. Secondary Efficacy Assessments

Secondary efficacy assessments in this study (Section 4) are intended to facilitate the collection and analysis of information such as response ($\geq 50\%$ reduction from baseline in the number of migraine headache days per month and number of monthly headache days) with data from the ePRO Diary (see above), and safety and tolerability of the study drug via analysis of TEAEs and SAEs.

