10.3.3.2. Secondary Analyses

Frequentist analyses for change from baseline in the monthly number of migraine headache days and change from baseline in the monthly number of headache days will be performed using the ANCOVA model. Comparisons between the treatments in rate of responders will be conducted using Cochran Mantel Haenszel tests that are stratified by the type of migraine.

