10.3.7.2. Analysis of C-SSRS Data

Suicide-related thoughts and behaviors occurring during treatment will be summarized based on responses to the C-SSRS consistent with the C-SSRS Scoring and Data Analysis Guide.

Additional details will be provided in the SAP.

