**Table 3.1. Objectives and Endpoints**

Objectives	Endpoints
Primary Objective	
To test the hypothesis that a single IV dose of LY3451838 is superior to placebo in the prevention of migraine in treatment-resistant migraine patients	The mean change from baseline in the number of monthly migraine headache days during the 1-month treatment phase (episodic and chronic migraine) a
Secondary Objectives	
To compare LY3451838 with placebo with respect to prevention of monthly headache days	The mean change from baseline in the number of monthly headache days during the 1-month treatment phase
To compare LY3451838 with placebo with respect to 50% response rate	The percentage of patients with $\geq 50\%$ reduction from baseline in monthly migraine headache days during the 1-month treatment phase
To evaluate the safety and tolerability of a single dose of LY3451838 in treatment-resistant migraine patients	TEAEs SAEs
To characterize the pharmacokinetics of LY3451838 following a single IV dose in treatment-resistant migraine patients	LY3451838 Cmax and AUC

The image consists of a large, bold, red text "CCI" centered on a solid black rectangular background. The font is a sans-serif style.

a Episodic migraine is defined as 4 to 14 migraine headache days and <15 headache days per 1-month period in the prospective baseline period. Chronic migraine is defined as at least 15 headache days per 1-month period in the prospective baseline period, of which at least 8 are migraine.

The image consists of a large, bold, red text "CCI" centered on a solid black rectangular background. The font is a sans-serif style.

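### SAP 5.11.4 leaves both secondary efficacy endpoints without a planned result although the diary data are in hand, and SAP 5.15.4 makes the promised C-SSRS summary optional without giving a reason

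*SAP*

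**What the plan says.** **Secondary efficacy.** Protocol 10.3.3.2 commits to a frequentist ANCOVA for change in monthly headache days. For responders it states: "Comparisons between the treatments in rate of responders will be conducted using Cochran Mantel Haenszel tests that are stratified by the type of migraine". SAP Table 3.1 keeps both endpoints; the first reads "The mean change from baseline in the number of monthly headache days during the 1-month treatment phase", and the second is the 50% response rate on migraine headache days. SAP 5.11.4 then states "Due to insufficient enrollment only the primary endpoint is to be evaluated", and adds that the secondary and exploratory data are held in the SDTM datasets should an analysis be wanted.

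**Source of the data.** Protocol 9.1.2 bases the secondary efficacy assessments (response and "number of monthly headache days) with data from the ePRO Diary") on the diary that also feeds the primary endpoint. SAP 5.11.1 refers to the "number of migraine headache days derived from the ePRO diary data for that 1-month period". SAP 5.11.2 reports that every patient exceeded 50% diary compliance in the treatment month and that "no subject has monthly migraine headache days set to missing". SAP 5.11.3 retains a further analysis of "monthly migraine headache day using post-baseline data to month 3".

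**C-SSRS.** Protocol 10.3.7.2 says: "Suicide-related thoughts and behaviors occurring during treatment will be summarized based on responses to the C-SSRS", and leaves the details to the SAP. SAP 5.15.4 gives no details and no reason; it says only that the data are available if an analysis is needed. Protocol 9.2.1 tells sites to leave the adverse event form as it is when a suicide-related event comes to light only through the C-SSRS, except that events that are serious or lead to discontinuation must be entered.

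**The concern.** The SAP states two secondary efficacy objectives and plans no result for either. The reason given, too few patients, bears on the power of a test. It does not bear on whether a count, a mean difference or an interval can be reported, and the same patients are judged sufficient for the primary model and for a three-month supplemental analysis.

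The C-SSRS gap is of a different kind. It is a safety output, for which low power is no ground for omission, and the enrollment reason appears only under efficacy. Because of the form rule in protocol 9.2.1, the adverse event tables cannot stand in for it completely.

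At stake are descriptive information on the trial's own objectives and the visibility of some suicidality findings. Leaving later analysis to be done as the need arises also leaves open which of these data will be reported.

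**Working it through.** The plan gives no figure to reproduce here. The check is mainly a comparison of texts, followed by an illustration of precision.

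**1. Is a result planned anywhere else?**

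| Item | Commitment | Planned output in the SAP |
|---|---|---|
| Change in monthly headache days | Protocol 10.3.3.2, ANCOVA | None (5.11.4) |
| 50% responders | Protocol 10.3.3.2, stratified comparison | None (5.11.4) |
| C-SSRS | Protocol 10.3.7.2, summary | None (5.15.4; absent from the 5.12.1 safety list) |

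SAP 5.17 plans no exploratory analyses, and the registry section, 5.18, itemises adverse events only.

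**2. Do the efficacy data exist?** Yes. SAP 5.11.4 says they are held. Responder status is a recoding of the baseline and month-1 migraine headache day counts already used in the primary model. Baseline cannot be zero in an eligible patient, because inclusion criterion 4 requires at least 4 migraine headache days. Headache days come from the same daily entries.

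**3. Which suicidality findings are lost?**
- Reported at the non-leading adverse event enquiry: on the form, so tabulated under SAP 5.12.1.
- Found only on the C-SSRS, and serious or leading to discontinuation: also entered on the form, so tabulated.
- Found only on the C-SSRS and neither of these: not on the form, and no C-SSRS table is planned. This is the gap.

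**4. How many visits?** In the Schedule of Activities the since-last-visit C-SSRS has 11 marks: Visits 2 to 11 (10) plus early discontinuation (1). Scheduled visits after the dosing visit are Visits 4 to 11, so 8. The protocol's promise concerns events during treatment, and SAP Table 5.1 ends the treatment period at Visit 5. On that definition the promise covers at least Visits 4 and 5 (2 of the 8), plus early discontinuation if it falls in that window.

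**5. Would estimates be usable?** Achieved enrollment is not stated, so this is illustrative. N = 60 is the planned size; N = 40 and 20, the SDs and the response rates are assumptions.

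*Headache days.* With 1:1 allocation and four model parameters, half-width = t(0.975, N−4) × SD × √(4/N).

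| Residual SD | N = 60 | N = 40 | N = 20 |
|---|---|---|---|
| 3 days | 1.55 | 1.92 | 2.84 |
| 5 days | 2.59 | 3.21 | 4.74 |

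*Responders.* Unstratified Newcombe 95% intervals, as a rough guide only (a stratified interval would differ somewhat):
- 30% v 10%: 6/20 v 2/20 gives 20 points (−5 to 43); 3/10 v 1/10 gives 20 points (−16 to 51).
- No placebo responder: 6/20 v 0/20 gives 30 points (8 to 52); 3/10 v 0/10 gives 30 points (−4 to 60).
- At a 10% placebo rate, the chance of no placebo responder is 0.9^(N/2): 0.9^30 = 4%, 0.9^20 = 12%, 0.9^10 = 35%.

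The intervals are wide but finite, even with an empty cell.

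**The case against.** **The sponsor disclosed the efficacy decision and gave a reason.** This stands. Protocol 10.3.1 also allows changes that do not touch a principal feature to be justified in the clinical study report. A reader might infer a breach of change control; the documents do not show one. But that clause does not supply the missing result, and no reason is given for the C-SSRS.

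**Estimates at an unknown, small N may say little.** This stands in part. Half-widths up to 4.7 days and an interval from −16 to 51 points are weak evidence, and achieved N could be lower still. That argues for labelling the results descriptive. It does not argue for leaving stated objectives unreported.

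**The SAP leaves room.** SAP 5.2 says efficacy data will be presented on the full analysis set, and 5.12.1 allows additional analyses as required. The first is essentially a population rule and the second commits to nothing specific.

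**The C-SSRS promise is narrower than its collection.** This stands. It would be tempting to say that a summary of all 8 post-dose visits was promised, but the wording about treatment, read with SAP Table 5.1, supports only the treatment period with confidence. For a single dose the phrase is ambiguous.

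**MSQ and HIT-6.** Protocol 10.3.7.1 says these will be analyzed, and SAP 5.15.2 and 5.15.3 make them optional. Calling this unexplained would go too far: the exploratory rows of the objectives table are not visible, the table's abbreviation note names both instruments, and if they are exploratory the reason in SAP 5.11.4 may already cover them.

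**Conclusion.** The point holds and should be fixed. Two of two secondary efficacy endpoints have no planned result although their data are available. The promised C-SSRS summary has become optional without a reason, so findings made only on that scale that are neither serious nor lead to discontinuation would appear in no planned table.

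The size is limited. The primary inference, the other safety summaries and PK (which has its own plan) are unaffected. SAP 5.4 plans no multiplicity adjustment, so what is lost on the efficacy side is descriptive information.

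Two stronger readings are not supported. SAP 5.11.2 and 5.11.4 were written with diary compliance and enrollment known, and a reader might infer selective reporting; nothing shows that treatment assignments were known or that results were chosen, so this is an open risk only. Nor is suicidality reporting removed altogether, since serious events, those leading to discontinuation and those reported spontaneously still reach the adverse event tables.

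The conclusion rests on the text. The precision figures depend on assumed N, SD and response rates and serve only to show that estimates are feasible.

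**What to change.** **SAP 5.11.4.** Keep the present statement for exploratory endpoints, limit it to those, and add:

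> Change in monthly headache days will be reported as the adjusted treatment difference with 95% CI from the ANCOVA with treatment, migraine type and baseline value, using the same 30-day normalization and 50% compliance rule as the primary endpoint. 50% responders will be reported as n (%) by arm, overall and by migraine type, with a risk difference stratified by migraine type (Mantel-Haenszel weights) and a 95% CI suited to small counts (e.g. stratified Newcombe). No hypothesis test will be done; results are descriptive because of reduced enrollment.

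Stratifying the responder difference follows the randomization and protocol 10.3.3.2. The normalization and compliance rules need stating because the SAP words them for migraine headache days only.

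**SAP 5.15.4.** Restore a by-arm descriptive summary, on the safety analysis set, of patients with any post-dose suicidal ideation or behavior on the C-SSRS. Give it for the treatment period and for all post-dose visits including follow-up, which settles the ambiguity about the window.

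**SAP 5.15.2 and 5.15.3.** If MSQ and HIT-6 are exploratory, a cross-reference to the reason in 5.11.4 may be enough. Otherwise give a reason or a by-arm descriptive summary.

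**Cost.** SAP wording and a few tables from data already collected. The intervals will be wide, possibly uninformative if very few patients were enrolled, and must be labelled descriptive.
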